8 QUESTIONNAIRES PATIENT

Patients will be advised to complete the questionnaires in a quiet area, and not to be disturbed while completing them. The patient will be advised to plan the time needed to complete the questionnaires for each visit. The patient will be able to complete the self-administered questionnaires during the consultation or immediately afterwards with the help of the health care team if necessary.

The questionnaires to be completed contemporaneously with the visits are as follows:

- Satisfaction questionnaire on the use of each insulin pump (at all visits)

There is no standardized and validated questionnaire in French to assess satisfaction with the use of an insulin pump. A specific questionnaire was therefore developed for the needs of this study.

The investigators will explain to patients the importance of completing the self-questionnaires, as per the protocol instructions.

9 DATA COLLECTION AND QUALITY CONTROL

9.1 INFORMATION SYSTEM

An online solution for managing the clinical observations of the study (eCRF) is available to the investigators of the study (Ennov Clinical).

The clinical data is hosted in a professional data center in France with backup and protection guarantees that comply with clinical research recommendations. The administration of the solution is managed by Axonal-Biostatem and Ennov.

A web platform (cloud) is managed by MEDTRUM to allow the collection of data from the pump. This platform is managed by MEDTRUM, and an application allows investigators to visualize the data and make extractions from a website (cloud).

A web-based (cloud) platform is used to collect data from each patient's FreeStyle Libre blood glucose meter. This platform is managed by Abbott and an application allows investigators to view the data and make extractions.

A web platform (cloud) Diasend® from Glooko is used to collect data from the Omnipod® pump. This platform is managed by Glooko and an application allows investigators to visualize data and make extractions.

No identifiable patient data will be collected in the eCRF, only the investigators will know the identity of the patients. Neither the sponsor nor the service provider will have access to the applications that allow access to patient data.

The processes implemented will comply with the European General Data Protection Regulation (GDPR). The exercise of investigators' and patients' rights can be done at [contact].

9.2 DATA ENTRY

9.2.1 Entered by the investigator

The patient's clinical data will be collected by the physician in an eCRF accessible via the Internet. Access to the eCRF will be individual by login and password, and the finalization of the data collection will require an electronic signature of the investigator.

The procedures for entering information into the eCRF will be explained to the physician during the study set-up visit. The physician should complete the eCRF as soon as possible after the information is collected, preferably on the same day as the visit.

Physicians will be identified in the application by a center number.

All patient data will be identified by a unique study-specific number in the eCRF database. Patients will also be identified in the eCRF by their initials (1st letter of first name and 1st letter of last name). Investigators are allowed to hold a correspondence list with patient's name data, but this information should not be included in the eCRF and should not be communicated to anyone, especially not to the Sponsor or the CRO provider.

9.2.2 Patient input

Data from the patient satisfaction questionnaires (self-questionnaires) will be collected on paper and entered by the investigating center into the eCRF.

9.3 DATA QUALITY CONTROL

Quality control of the database will be carried out throughout the conduct of the study in order to allow the final database to be frozen within a short time frame.

Correction requests will be generated automatically by the system. The CRO provider staff will be able to manually generate specific correction requests from the eCRF if necessary.

The study logistics center (Axonal-Biostatem) will ensure regular communication with investigators to request a response to unresolved eCRF correction requests.

The investigating physicians will be consulted to obtain their agreement for any correction of their data. The final data must be checked and approved by the investigator with his/her electronic signature.

9.4 FINAL FREEZE OF THE DATABASE

After the database has been declared "clean" for analysis (i.e., the most complete and accurate), the database will be frozen and saved before statistical analyses are launched, a freeze certificate will be documented.

Any changes to the database after this date can only be made by joint written agreement between the Study Sponsor and the statistician.

10 EVALUATION CRITERIA AND FOLLOW-UP

10.1 PRIMARY ENDPOINT

The primary end point was the estimation of HbA1c from the mean of glucose measurements over the last 10 weeks of follow-up.

Blood glucose levels will be obtained from the FreeStyle Libre continuous glucose sensor, extracted from the application provided by the manufacturer (already used in routine) and reported by the investigator in the eCRF. The investigator will be asked to print the measurements from the software to facilitate the monitoring of the reported data.

There will be no recalculation of the estimated HbA1c.

We chose to assess HbA1c from a sensor measurement that is a good estimate of mean blood glucose. The evolution of the classical HbA1c level is not informative on the time spent in hyper or hypoglycemia (whether or not the latter are symptomatic) and does not reflect glycemetic variability. Moreover, if the study by Nathan¹⁷ underlines the reliability of the estimation of HbA1c over 14 days of continuous measurements with a sensor, as well as the ADA Recommendations²⁵ in 2017, more recently those of the "International Consensus on Time in Range"²⁶ published in 2019 remind the limits of the HbA1c criterion in the laboratory. The evolution of the monitoring of the effectiveness of insulin treatment is increasingly oriented towards average glycemia and "Time in Range" (time spent within the target values).

We propose to evaluate, as a secondary endpoint, the evolution of HbA1c measured in the laboratory from a blood sample at the beginning and at the end of the study, as well as the Time in Range which is automatically calculated from the data of the FreeStyle Libre reader.

10.2 SECONDARY ENDPOINTS

The secondary endpoints were:

❖ HbA1c:

- Value measured in the laboratory from a blood sample taken before the D0 visit and just before the 3-month visit

❖ Glucose Level Measurements

- Average Glucose Measurements over each period and over the entire study duration
- Minimum and maximum values
- Time in range expressed as a % (see ADA and International Consensus on Time in Range recommendations^{25,26})

These values are automatically calculated by the FreeStyle Libre software and will be reported by the investigator.

❖ Glycemic events

- Number of symptomatic and non-symptomatic hypoglycemic episodes during the evaluation period, broken down by severity level (see below)

- Number of symptomatic and non-symptomatic hyperglycemia events during the evaluation period, broken down by severity level (see below)

This information is derived from the FreeStyle Libre data and the data entered by the patient in the PDM.

The definition of hypoglycemia and hyperglycemia is the ADA consensus definition²⁵ :

Outcome	Definition
Hypoglycemia	Level 1: glucose <70 mg/dL (3.9 mmol/L) and glucose \geq 54 mg/dL (3.0 mmol/L) Level 2: glucose <54 mg/dL (3.0 mmol/L) Level 3: a severe event characterized by altered mental and/or physical status requiring assistance
Hyperglycemia	Level 1—elevated glucose: glucose >180 mg/dL (10 mmol/L) and glucose \leq 250 mg/dL (13.9 mmol/L) Level 2—very elevated glucose: glucose >250 mg/dL (13.9 mmol/L)
Time in range	Percentage of readings in the range of 70–180 mg/dL (3.9–10.0 mmol/L) per unit of time

❖ Device tolerance

- Local skin tolerance at the pump site (adhesive hold) and at the FreeStyle Libre blood glucose sensor site (adhesive hold).
- Any local or systemic safety issues should be reported during the study, including the additional one-month phase at the end of the study for patients in the "OmniPod" group

❖ Incidents with devices

- Any type of incident involving the operation of the medical devices used, particularly for pumps: removal, control problems, transmission difficulties, obstructions, leaks, etc.

❖ Patient satisfaction

- Self-questionnaire evaluating satisfaction with the use of the device (pump+PDM)
- Final question regarding patient preference between the Medtrum device and the Insulet device

❖ Insulin treatment

- The insulin treatment used should be documented
- Delivered insulin doses will be derived from the pump's data logging
- Although not allowed in the study, possible additional insulin injections with a pen will be documented if applicable

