1 INTRODUCTION

1.1 INTRODUCTION AND RATIONALE FOR THE STUDY

The treatment of patients with type 1 diabetes and some type 2 diabetics is based on insulin therapy that mimics the physiological secretion of the pancreas through a basal/bolus regimen, obtained either by daily multi-injections or by external insulin pump. The objective of this basal/bolus regimen is to approach normoglycemia in order to prevent :

- in the long term, chronic complications of diabetes;
- in the short term, acute complications of diabetes which are metabolic emergencies (including coma): related either to hyperglycemia and ketoacidosis or to hypoglycemia.

Diabetes is a serious disease because of its complications. However, these complications can be prevented and/or mitigated with sustained metabolic control of blood glucose. This control aims to achieve an A1C level of less than 7 or 7.5% (the percentage being different depending on the recommendation and the type of patient) without increasing hypoglycemic episodes. A position paper from the Société Francophone du Diabète published in 2009¹⁴ states that external insulin pumps have proven their effectiveness for years as an intensive treatment of diabetes by improving glycemic control and reducing hypoglycemia.

Overall, the indications for pump therapy can be summarized as follows:

- need for an intensive program (at least 3 injections per day, 3 self-monitoring of blood glucose per day)
- poor glycemic control despite intensive treatment (A1C > 7.5%, 2 episodes of severe hypoglycemia or unexplained coma within a year and/or 4 moderate hypoglycemia per week)
- variability of insulin requirements.

Absolute contraindications are rare and include severe psychiatric disorders, rapidly progressing ischemic or proliferative retinopathy (prior to laser treatment), and high magnetic field exposure.

In the current decades, there have been several innovations in diabetes management. Pumps have become smaller, less invasive and easier to use. They also have the potential to have sensors and algorithms built into them to be part of a loop that should lead, in the longer term, to an artificial pancreas.

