4.2 SECONDARY OBJECTIVES

The secondary objectives are to describe the following information:

- HbA1c values measured at the medical and biological laboratory at the beginning and end of the study
- Glucose measurements (minimum, maximum, mean/median, standard deviation, off-target value, time in range[Time in Range] , variability)
- Glycemic events (hypoglycemia and hyperglycemia - as defined by the ADA²⁵ , coma, other complications)
- Skin and general tolerance
- Technical incidents with the device
- Overall patient satisfaction, on the overall population, in each arm and comparison between the two arms
- Insulin treatment compliance

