7.2 EVALUATION SCHEDULE

The evaluation schedule is presented below in **Table 2**.

	screening	inclusion	1M	3M	1M additional
					Omnipod patients only
seeking patients already using Insulet + FreeStyle Libre	X				
ensure availability of HbA1c <1M and blood glucose results	X				
informing the patient		X			
signature consent		X			
verification of inclusion and exclusion criteria		X			
randomisation of pump type		X			
socio-demographic data		X			
history of the disease		X			
HbA1c values and A1c estimates at inclusion		X			
major blood glucose events last month and last 6 months		X			
supply of MEDTRUM equipment		X			X
verification of the correct use of devices		X	X	X	
possible incidents with the devices			X	X	X
adverse events			X	X	X
collection and reporting of blood glucose data and events		X	X	X	X
collection and reporting of pump data			X	X	X
pump and PDM satisfaction questionnaire		P	P	P	P
P = questionnaire filled in by the patient					

Table 2 Evaluation Schedule

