7.3 VISIT 1: INCLUSION VISIT WITH INFORMED CONSENT

No study-specific procedures should be performed until informed consent has been obtained from the patient.

Study procedures at Visit 1 include the following assessments:

- Provide verbal information about the study procedures and objectives as well as those presented in the package insert, and ensure that the patient has the opportunity to ask questions
- Obtaining the signature of the informed consent
- Collect the following data using the eCRF:
 - Socio-demographic data
 - Age of diabetes, type, age of insulin therapy
 - HbA1C at the time of insulin pump prescription
 - Current model of pump used by the patient
 - Patient satisfaction with the current pump
 - Type of insulin used
 - Last HbA1C value less than one month old
 - Available glucose measurements (average of glucose measurements, estimated HbA1c, time in range)
 - Number of major glycemic events in the past month (as defined by the ADA) and in the past 6 months
 - Randomization of the patient in the pump group "Omnipod" or "Medtrum"

7.4 VISIT 2 (4 WEEKS): FOLLOW-UP VISIT AFTER 4 WEEKS OF PUMP USE.

- Collect tolerance data and possible adverse events, and report them as required from the eCRF
- Verify the conditions of use of the devices by the patient

- Collect time-stamped records of glucose values (as well as HbA1c estimated from average glucose measurements) and glycemic events, hypoglycemia and hyperglycemia, and insulin doses administered, from software provided by manufacturers
- Collect technical incidents with the device (catheter occlusion, alarms, pump detachment, pain, allergy, etc.)
- Patient satisfaction with their insulin delivery system
- Confirm or schedule the date of the V3 visit after 3 months of use
- Record all relevant data in the eCRF.

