3.2 SECONDARY OBJECTIVES

Secondary objectives were to describe the following information:

- HbA1c values measured at the medical and biological laboratory at the beginning and end of the study
- Glucose measurements (minimum, maximum, mean/median, standard deviation, out-of-target value, time in range, variability)
- Glycemic events (hypoglycemia and hyperglycemia as defined by the ADA, coma, other complications)

- Skin and general tolerance
- Technical incidents with the device
- Overall patient satisfaction, in the overall population and in each arm
- Insulin treatment compliance

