7.4.2 Secondary endpoint analyses

Analyses will be performed on the ITTm population.

Each variable will be described globally and by pump group.

The secondary endpoints are:

1. HbA1c

The evolution of HbA1c (measured in the laboratory) between D0 and 3M will be described, and a comparison between the groups will be made using a Student's t test or a Mann and Whitney test.

2. Glucose level measurement

The mean blood glucose level and its standard deviation (Blood Glucose Deviation SD) will be described over each period (between V1 and V2, then between V2 and v3, then between V3 and V4) and over the total duration of the study (mean, median, standard deviation, Q1-Q3, minimum and maximum). The coefficient of variation of glucose values will also be described.

The evolution of the average blood glucose level compared to baseline will be described at each visit.

FSL wear time (%) will be described.

The % of blood glucose values spent in target (time in range: [70; 180]), hypoglycemia (<70mg/dl), and hyperglycemia (>180 mg/dl) will be described over each time period in each pump group and in the total population.

For these criteria, comparisons between groups will be made using the Student or Mann-Whitney test.

3. Glycemic events

The number of hypoglycemic events will be described overall and in each period by severity level (according to ADA consensus definitions) overall and in each pump group.

Comparisons between groups will be made using Student or Mann-Whitney tests.

The % of time spent in hyperglycemia will be described overall and over each period and in each pump group. Comparisons between groups will be made using Student's t test or Mann and Whitney test.

4. Device tolerance

The analysis of this criterion is detailed in section 7.4 of this document.

5. Incidents with devices

The following criteria will be described for each period and by pump group (after reclassification):

- Pump occlusion (yes; no)
 - If yes, number of times
- Pump detachment (yes; no)
 - If yes, number of times
- Complete stop / breakage of the pump (yes; no)
 - If yes, number of times
- Other pump malfunction (yes; no)
 - All other possible malfunctions will be listed.

6. Patient satisfaction

The following criteria will be described for each period and by pump group:

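### Follow-up has no dedicated, causality-independent item for Level 3 hypoglycaemia, ketoacidosis or coma, so counts by arm would be incomplete

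*Protocol*

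**What the plan says.** The introduction (Protocol 1.1) gives the short-term purpose of insulin therapy as preventing "acute complications of diabetes which are metabolic emergencies (including coma): related either to hyperglycemia and ketoacidosis or to hypoglycemia". The secondary objectives carry this through: under glycaemic events, Protocol 4.2 lists "coma, other complications", and SAP 3.2 has the same entry: "Glycemic events (hypoglycemia and hyperglycemia as defined by the ADA, coma, other complications".

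**Definitions and source.** The table in Protocol 10.2 has three levels of hypoglycaemia and two of hyperglycaemia. The third hypoglycaemia level is "Level 3: a severe event characterized by altered mental and/or physical status requiring assistance". Ketoacidosis and coma do not appear. The stated source is: "This information is derived from the FreeStyle Libre data and the data entered by the patient in the PDM".

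**Inclusion.** Protocol 7.3 collects "Number of major glycemic events in the past month (as defined by the ADA) and in the past 6 months". Table 2 in 7.2 ticks the row "major blood glucose events last month and last 6 months" at inclusion and at no later visit.

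**Follow-up.** The V2, V3 and V4 lists (Protocol 7.4 to 7.6) collect time-stamped glucose values and glycaemic events. At V2 the source is expressly the manufacturers' software. The same lists collect tolerance data and adverse events, and 13.2.1 has the investigator interview the patient about adverse events at each assessment.

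**Analysis.** SAP 7.4.2, item 3 states: "The number of hypoglycemic events will be described overall and in each period by severity level", followed by between-group tests. It covers hyperglycaemia only as percentage of time and has no line for ketoacidosis, coma or other complications.

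**The concern.** Level 3 is a clinical category. A glucose trace can show a value below 54 mg/dL, but not whether the patient needed another person's help. The row promised in SAP 7.4.2 therefore depends on what patients happen to enter in the handset, and neither document says that such an entry is possible or that the two pumps' handsets offer the same one. Ketoacidosis and coma have no entry in the definition table, no follow-up item of their own and no analysis line.

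A low Level 3 count could then be reported by arm as a finding about the new pump when it partly reflects how events were sought. The severe events that do reach the database would mostly arrive through the adverse-event route, after a judgement on whether the device was responsible. The trial is open-label, so that judgement is made by people who know the arm. Severe acute events are also among the things that the Supervisory Committee would want complete for its benefit/risk review (Protocol 13.4).

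**Working it through.** **Step 1. Can the stated source supply each category?**

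| Category | Sensor data | PDM entry by patient | Own follow-up question | SAP 7.4.2 item 3 |
|---|---|---|---|---|
| Hypoglycaemia Levels 1 and 2 | Yes, glucose thresholds | Possible | Not needed | Yes |
| Hypoglycaemia Level 3 | No, no threshold in the definition | No field described | None | Yes, as one of the severity levels |
| Ketoacidosis | No | No field described | None | None |
| Coma | No | No field described | None | None |

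The inclusion count does not fill the gap. It is not repeated, it names neither ketoacidosis nor coma, and the baseline list in SAP 7.3 does not include it.

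**Step 2. What would the safety route catch?**

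- Protocol 13.2.1 provides an interview at each assessment, but keeps adverse events unrelated to the device or its procedure out of the eCRF.
- Protocol 13.2.2 first limits the duty to notify to serious events related to the device. It later requires the SAE form for every SAE whatever the causal link. Both cannot be the rule.
- Under the SAE definition in 13.1, a hospitalised ketoacidosis or a coma would qualify. A Level 3 episode resolved at home by a relative need not, although the medical-judgement clause could bring it in.
- SAP 7.5 puts reported events into a listing and a coded table by pump group. The derived flag in SAP 4.4.3 combines any other adverse event with itching and redness. No rule carries these records into the Level 3 row or the coma objective.

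**Step 3. How many events are at stake?** The documents give no figure for severe events, so there is none to reproduce. The sample size concerns the primary endpoint only and does reproduce: 2 × (1.960 + 0.842)² × 0.55² / 0.4² = 29.7, so 30 per group. With SD 0.8 it is 62.8, so 63 per group. Neither result bears on this point.

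Inputs: 100 patients included (SAP 5.1), 1:1 allocation and 12 weeks of randomised follow-up (Protocol 2.1).

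- Exposure: 100 × 12/52 = 23.1 patient-years, or 11.5 per arm. Without the four patients discharged because of COVID-19 (SAP 7.1.3), 96 × 12/52 = 22.2.
- Expected events per arm = 11.54 × rate. The rates are assumptions, shown as a range. Power is for a two-sided 5% conditional exact test with full capture.

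| Assumed rate per patient-year | Expected per arm | Total, equal rates | Power, rate doubled in one arm | Power, rate tripled |
|---|---|---|---|---|
| 0.05 | 0.6 | 1.2 | 0.1% | 0.5% |
| 0.2 | 2.3 | 4.6 | 6% | 21% |
| 0.5 | 5.8 | 11.5 | 21% | 61% |

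- If 50 patients in one arm have no event, the two-sided 95% upper limit is 1 − 0.025^(1/50) = 7.1% of patients. That limit is valid only if every event was sought.
- At the lowest assumed rate, the chance of no event in either arm is exp(−23.08 × 0.05) = 0.32 even with perfect capture.

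**The case against.** The strongest reply is that follow-up does enquire. Table 2 schedules adverse events, and the collection of glucose data and events, at every follow-up visit. The investigator interviews the patient each time. Protocol 10.2 asks for any local or systemic safety issue. One sentence of 13.2.2 requires a form for every SAE, and the independent committee in 13.4 adjudicates them. The definition of a related event in 13.2.1 is wide, so many severe glycaemic events on a pump could be classed as related and entered. Reported cases would then appear by arm in the coded table of SAP 7.5.

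All of that stands, and it rules out several stronger readings that a reader might infer:

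- *Severe events are asked about only at inclusion.* The adverse-event interview contradicts this, and the inclusion item does not name ketoacidosis or coma in any case.
- *The Level 3 count will be near zero.* Neither the eCRF pages nor the PDM event fields are shown, so an undercount is likely but its size is unknown.
- *The handsets capture events differently by arm.* The only handset differences stated that could matter concern the screen. Nothing is said about event entry.
- *The trial cannot compare these events because of the capture gap.* Step 3 shows that about 23 patient-years would not support a powered comparison even with full capture.

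The reply does not supply a solicited item independent of causality, a source for the Level 3 row, or an analysis of coma and other complications. It also relies on the SAE sentence that another sentence in the same section contradicts.

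**Conclusion.** The point holds as one of incomplete capture and missing traceability. Followed as written, the plan would give severe-event counts by arm that depend on unprompted patient entries and on adverse events filtered by judged device-relatedness in an open-label trial. A stated secondary objective would have no analysis of its own. The primary analysis is unaffected.

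The absolute numbers are small: about 1 to 12 events in total over V1 to V3, assuming 0.05 to 0.5 events per patient-year and 12 weeks of follow-up for all 100 patients. With so few events, missing a handful could change what the report says, yet full capture would still support description only. The share that would be missed cannot be derived from the documents.

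**What to change.** 1. At V2, V3 and V4, add one solicited item, identical in both arms and completed whatever the judged causality: number and dates of Level 3 hypoglycaemia, ketoacidosis and coma since the last visit. Put the definitions used beside it, because the table in Protocol 10.2 has none for the last two. This is a new item, since the inclusion question names neither.
2. In Protocol 10.2 and SAP 4.4.2, state that Level 3 comes from this item and Levels 1 and 2 from the sensor.
3. Reconcile the two SAE sentences in Protocol 13.2.2.
4. In SAP 7.4.2, item 3, report by arm for V1 to V3 the number and percentage of patients with at least one event, and events per patient-month, with confidence intervals. Label this as descriptive. Keep V4 separate, because by then the Omnipod arm is using the Medtrum pump.

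The cost is one eCRF item at three visits, two source statements and one table. The drawback is that these events rest on patient recall, which in an open-label trial may itself differ by arm. Asking for dates limits this but does not remove it.

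The SAP was written after inclusion had ended, so some or all visits may be over. In that case, recover what the SAE forms and medical records hold before the freeze. State in the report that episodes treated at home may be missed and that a low count is not evidence of absence.
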